Objectives:	The objective of this observational prospective study is to systematically document the clinical outcomes of Zimmer MotionLoc Screws for Periarticular Locking Plate System applied to distal tibia fracture treatment and confirm safety and performance of the screws.
Endpoints:	
Primary endpoint: Radiologic & clinical fracture healing at three months post-surgery.
 
Secondary endpoints:
 
 • Complications • Radiologic & clinical fracture healing at 6 weeks, 3, 6, and 12 months post-surgery. • Callus size & distribution at 6 weeks, 3, 6, and 12 months post-surgery.
Target Population:	Patients with distal tibia fractures (AO 43-A and C) requiring surgical intervention eligible for locked plating.
Study Design:	Prospective, global, multi-center, non-randomized, non-controlled
Number of Cases:	Patient enrollment is limited to one year or 40 subjects whichever is reached first. Per site enrollment will be limited to 15 subjects.
Length of Study:	2 years (1 year enrollment plus 1 year follow-up): Required follow-up visits at 6 weeks, 3, 6, and 12 months post-surgery.
Study Device:	Zimmer® Periarticular Distal Tibial Locking Plates (medial and/or lateral) in conjunction with Zimmer® MotionLoc® Screw for the Periarticular Locking Plate System.
Scores:	FIX-IT
Documentation:	Electronic Case Report Forms
Statistical Reporting:	Data collected will be summarized and reported to each participating investigator. Statistical analysis will be conducted by Zimmer Biomet or its designee.

II. Introduction

The optimal treatment for distal tibia fractures remains controversial. A recent systematic literature review found a reduced risk for malalignment for plate fixation compared to intramedullary nailing [2]. However, for bone union, wound complications and superficial infection or deep infection no statistically significant differences were identified.

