Patient eligibility for enrollment will be determined for consenting candidates based on the inclusion/exclusion criteria. Patients must meet all of the inclusion criteria and none of the exclusion criteria in order to be offered enrollment into the study. Determination of eligibility may include an interview to assess significant patient surgical/medical history, history of present illness/injury, evaluation of present pain and functional capacity, and a radiographic assessment. All eligible patients will be offered enrollment into the study. For the purposes of this clinical study, patients will be considered subjects after enrollment has been completed.

Subject Enrollment Log

A Subject Enrollment Log must be maintained throughout the study and is included in the Investigator Binder. All patients enrolled in the study must be entered into the Enrollment Log and the "Inclusion/Exclusion" form must be completed. Patients must be entered into the Enrollment Log sequentially.

Baseline/Preoperative Assessment

Following enrollment, demographic and injury classification data will be entered into the “Demographic Information & Injury Classification” set of forms.

Surgical Technique

Implantation will be performed in accordance to the manufacturer’s surgical technique. The distal articular segment will be fixed to the plate(s) (medial and/or lateral *Zimmer* Periarticular Distal Tibial Locking Plate) with the appropriate number of standard locking screws. All fractures will be treated with a “bridge plating” strategy - working length (empty screw holes between the distal and proximal segment, see Figure) is up to investigator/surgeon discretion. A minimum of three MotionLoc screws will be applied into the proximal shaft segment. No inter-fragmentary lag screws are permitted across non-articular fractures.

[figure not shown]

Figure 2: Working length

After surgery, intraoperative data will be entered into the “Operative Information” set of forms.

Postoperative Care

Weight bearing will be at the surgeon’s discretion based on the degree of fracture healing.

Surgery until Discharge

After surgery, but before the subject leaves the hospital, standard anteroposterior and lateral x-rays of the operated side must be obtained and the “Discharge” set of forms must be completed.

Follow-up Procedures (Data Collection)

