Follow-up evaluations will be performed at 6 weeks (± 14 days), 3 months (± 14 days), 6 months (± 30 days) and 12 months (± 30 days) post-surgery. Standard anteroposterior and lateral x-rays of the operated side must be obtained at each follow-up. If the treating surgeon is unable to adequately assess cortical healing due to radiographic obstruction of the implant(s), additional x-ray(s) should be performed. At 3 months a CT scan of the fracture site must be performed in addition. The “Follow-up” set of forms must be completed at each follow-up time point. This includes the assessment of radiologic fracture healing. At 6 weeks, 3, 6 and 12 months, the surgeon must assess the FIX-IT Score and document on the corresponding set of forms. At the 12

month follow-up the “Study Completion” form must be completed additionally. Copies of the original x-ray films and CT scans must be sent to the Sponsor.

Patient Withdrawal

Patient withdrawal has to be documented on the “Study Completion” form. In particular the reason for withdrawal must be documented. The occurrence of any of the following situations gives reason to withdraw a patient from the study:

- Voluntary patient withdrawal. Patients are at liberty to withdraw from the study at any time and for any reason without affecting future treatment.
- Development of a concurrent condition which would interfere with the patient's continued participation.
- Reoperation including complete removal of study device(s).
- Patient is non-compliant.

Lost to Follow-up

Patients will be considered lost to follow-up after they have missed a visit and a reasonable number of attempts to locate and evaluate them have failed. This has to be documented on the “Study Completion” form and in particular the reason should be documented. Patients lost to follow-up will not be replaced within the study.

Minimization of Subjects Lost to Follow-Up

Subject follow-up is extremely important for the conduct of a clinical study. The expectation is to maintain the highest rate of follow-up compliance possible throughout this study. No replacement is foreseen for any patient lost to follow-up. In an effort to minimize lost-to-follow-up subjects, the following recommendations and/or study requirements are essential to ensure proper patient selection and compliance:

1. Patient Eligibility: Subjects will be selected according to the inclusion/exclusion criteria detailed in Section 8 and are expected to return for all follow-up visits.

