If a device has to be removed¹, the investigator will choose the best revision treatment method for the subject. Before revision surgery, the Investigator must document any significant radiographic findings related to the need for revision. Additionally, once the revision surgery has been completed, the Investigator must complete an Adverse Event CRF, as well as a Study Completion CRF, terminating the subject from the study.

¹Device removal after fracture healing, upon patient request or as part of standard treatment, is not considered a “Recommended Revision Procedure”.

Explanted Device Return

All components removed, except the devices removed after fracture healing upon patient request or as part of standard treatment, should be returned to Zimmer Biomet for analysis. The Investigator must notify the Clinical Study Manager prior to the return of any device. Properly prepared specimens are to be sent to:

Zimmer Biomet
Attention: Product Services Department
[name]
[name]

VII. Statistical Methods

General Statistical Methods

Considering the inclusion and exclusion criteria, per study site an enrollment of 5 patients in one year can be expected. Within one year of enrollment at 8 study sites this equals to 40 patients in total. For the purpose of this observational study this number of patients is considered to be sufficient to document first clinical outcome and assess safety and performance. Collected data will be presented descriptively. For categorical data, frequency and percentage will be calculated. For continuous data, mean, standard deviation, median, minimum and maximum will be calculated.

Comparative assessment

For comparative assessments of any non-parametric data (e.g. score between different follow-up time points) the Wilcoxon test will be used for paired, and the Mann-Whitney test for unpaired data. A significance level of $p=0.05$ will be set.

VIII. Risk Analysis

Zimmer MotionLoc Screws for the *Zimmer* Periarticular Locking Plate System have been commercially available since April 2014. The devices involved are used in accordance with the cleared indications. There are no anticipated risks specific to study participation other than the potential loss of confidentiality. There are no experimental procedures in this study and participation is not anticipated to affect the medical treatment of enrolled subjects.

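### The two study-exit rules for reoperation differ and 'device' is undefined, so a partly revised, unhealed subject may be followed at one site and terminated at another

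*Combined protocol and SAP*

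**What the plan says.** Section VI, Patient Withdrawal, introduces its list with "The occurrence of any of the following situations gives reason to withdraw a patient from the study". The one entry about reoperation is "Reoperation including complete removal of study device(s". The other entries are the patient's own decision, an interfering concurrent condition, and non-compliance. Partial removal is not mentioned.

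Section VI, Recommended Revision Procedure, starts from a different trigger, "If a device has to be removed". It leaves treatment open: "the investigator will choose the best revision treatment method for the subject". After the revision, however, "the Investigator must complete an Adverse Event CRF, as well as a Study Completion CRF, terminating the subject from the study". A footnote takes removal after healing, at the patient's request or as routine care, out of this procedure.

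The implant is an assembly. The synopsis gives the study device as medial and/or lateral plates "in conjunction with Zimmer® MotionLoc® Screw for the Periarticular Locking Plate System", and Surgical Technique adds: "A minimum of three MotionLoc screws will be applied into the proximal shaft segment". Section VII plans frequencies and percentages for categorical data and has no rule for subjects whose participation ends early.

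**The concern.** With one or two plates and at least three MotionLoc screws, part of the construct can be removed or exchanged while the rest stays in. In an unhealed fracture, one section gives no specific reason to stop following such a subject. The other, read literally, requires the subject to be terminated. About 8 sites could each choose differently in good faith.

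These subjects matter because the study is meant to show how the screws perform, and a fracture that needed a partial revision while still carrying study hardware is direct evidence on that. Early exit would remove its later healing and callus assessments and any later complications. A revision before the 3-month visit would affect the primary endpoint as well as the secondary ones.

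**Working it through.** **Step 1: the two rules side by side.**

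| Situation | Patient Withdrawal | Recommended Revision Procedure |
|---|---|---|
| Part of the construct removed, fracture unhealed | Not a listed reason | Termination required if a plate or screw counts as a device; not triggered if only the whole construct does |
| Whole construct removed, unhealed | Reason to withdraw | Termination required |
| Bilateral case with study constructs in both legs, one removed, unhealed | Unclear whether removal is complete | Termination required |
| Whole construct removed after healing | Reason to withdraw, no exemption | Exempt by the footnote |
| Reoperation with nothing removed | Not a listed reason | Not triggered |

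The rules can diverge in the first, third and fourth rows. Their force differs too: the withdrawal list is permissive, while the revision text is mandatory.

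**Step 2: what the protocol means by a device.** No section defines it.
- For the whole construct: the synopsis describes plates and screws together as the study device, and Explanted Device Return speaks of components when it means parts.
- For individual parts: the same paragraph carves exempt devices out of removed components, Section IV describes the screw alone under its device description, and the withdrawal entry allows for a plural.

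Both readings are workable. The whole-construct reading would reconcile the first row, but not the third or fourth.

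**Step 3: size.** The plan's own total reproduces: 5 patients per site × 8 sites = 40. Section V sets a floor of 30. Three inputs are assumptions, because the documents do not give them:
- k, the number of partly revised subjects;
- p, the proportion healed among the others, taken as about 90%;
- that terminated subjects leave the denominator.

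Let n be the number enrolled and h the number healed among the n − k others, so p = h/(n − k). Full follow-up of the others is assumed.
- Dropped: h/(n − k).
- Followed, none of the k heal: h/n. Dropping them raises the percentage by p × k/n.
- Followed, all of the k heal: (h + k)/n. Dropping them lowers it by (1 − p) × k/n.

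| n | k | Dropped | Followed, none heal | Followed, all heal |
|---|---|---|---|---|
| 40 | 0 | no effect | no effect | no effect |
| 40 | 1 | 35/39 = 89.7% | 35/40 = 87.5% | 36/40 = 90.0% |
| 40 | 3 | 33/37 = 89.2% | 33/40 = 82.5% | 36/40 = 90.0% |
| 30 | 1 | 26/29 = 89.7% | 26/30 = 86.7% | 27/30 = 90.0% |
| 30 | 3 | 24/27 = 88.9% | 24/30 = 80.0% | 27/30 = 90.0% |

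One subject who does not heal moves the result by 2.2 points (n = 40) or 3.0 points (n = 30). If that subject heals, the shift is about 0.3 points in the other direction.

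The per-subject figure falls with p. At about 80% healing and n = 40 it is 31/39 − 31/40 = 79.5% − 77.5% = 2.0 points. At about 60% it is 23/39 − 23/40 = 59.0% − 57.5% = 1.5 points.

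**The case against.** The best defence is that a device means the whole plate-and-screw construct, so that both sections concern its removal and agree on partial revisions. That reading is possible, and it means the fault is an undefined term with two workable meanings rather than two settled, opposed rules. It does not remove the problem, because nothing in the protocol tells a site to adopt it and some of the wording points the other way.

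Three further objections stand and limit the point.
- The withdrawal list is permissive and silent on partial removal. That a partly revised subject stays in to 12 months is inferred from that silence, and another listed reason might apply.
- A reader might infer that fixation failures would vanish from the results. The documents do not support that. The revision section requires radiographic findings to be documented before surgery and an adverse event form after it, removed components should be returned for analysis, and Section IX requires complications and their outcomes to be recorded. The event therefore reaches the complications endpoint under either reading.
- A reader might infer a definite inflation of several points from the k = 3 rows. Those rows need three partial revisions, none of which heal, and a denominator rule that the protocol does not state. Zero is a realistic count: the femur study cited in Section II had no implant or fixation failure in 31 fractures, although in a different bone, with a different plate system and over 6 months. The exact two-sided 95% upper limit for 0/31 is 1 − 0.025^(1/31), about 11%, and only part of such failures would be partial removals before healing.

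The analysis is also descriptive with no success threshold, so no stated decision turns on these points.

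**Conclusion.** The concern holds as an inconsistency in the study-exit rule, centred on an undefined term. Sites may follow or terminate a partly revised, unhealed subject differently, and removal after healing is handled differently in the two sections. What is at risk is later healing, callus and complication data, not the record of the revision itself.

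The healing percentage is biased upward only if terminated subjects leave the denominator and their fractures do not heal. The size then is up to about 2 to 3 points per affected subject at 40 or 30 subjects, given about 90% healing in the rest. It is near zero if the revised fractures heal, and zero if no partial revision occurs. The documents cannot say which of these will happen. The change is worth making because these few subjects are informative about the screws and the correction is cheap.

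**What to change.** Reconcile Patient Withdrawal and Recommended Revision Procedure so that both state one study-exit rule. Specifically:
- **Definition.** Define the study device in terms of plate, screws and construct, and say how the definition applies when both legs are treated.
- **Removal after healing.** Apply the revision footnote to the withdrawal list as well.
- **Data collection.** Keep subjects who retain part of the construct on the visits already scheduled to 12 months, and record the revision date and the components removed or exchanged.
- **Analysis.** In Section VII, state that every subject revised before healing, partly or completely, is reported in the 3-, 6- and 12-month healing denominators, flagged as revised, and not dropped.

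These changes concern follow-up and reporting only; the choice of revision treatment remains with the investigator. The cost is a few sentences of protocol text, completion of scheduled visits for a handful of subjects at most, and possibly slightly less favourable healing percentages.

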In the last decade locking plates gained popularity not only for distal tibia fractures but fracture treatment in general. Recent studies raised concerns because of the inherent stiffness of these locking devices and found they might suppress fracture healing [3][4][5]. To address this issue the concept of Far Cortical Locking (FCL) was developed [6][7] and has been commercially available since 2010 in the *Zimmer MotionLoc* Screw for NCB[®] Polyaxial Locking Plate System and since 2014 in the *Zimmer MotionLoc* Screw for *Zimmer* Periarticular Locking Plate System (Zimmer Inc.).

FCL screws lock rigidly into the plate and into the far cortex, but retain a controlled motion envelope in the near cortex. The screws have an elastic shaft portion that can deflect within this motion envelope. This flexion of FCL screw shafts induces symmetric axial motion at the fracture site in response to load bearing. FCL screws are optimized to reduce the initial stiffness of a locked plating construct while retaining its construct and fixation strength. *MotionLoc* Screws for *Zimmer* Periarticular Locking Plate System reduce the locked plating construct stiffness by more than 58% while retaining construct strength [8].

Recently, a prospective observational clinical study in 31 distal femur fractures treated with *Zimmer MotionLoc* Screws for NCB Polyaxial Locking Plate System has shown a fracture healing rate of 97% (30 out of 31) after a 6 month follow up period with no implant and fixation failure.

The purpose of this observational prospective study is to systematically document the clinical outcomes of *Zimmer MotionLoc* Screws for Periarticular Locking Plate System applied in distal tibia fracture treatment and confirm safety and performance of the screws.

III. Study Objectives

The objective of this observational prospective study is to systematically document the clinical outcome of *Zimmer MotionLoc* Screws for Periarticular Locking Plate System applied in distal tibia fracture treatment and confirm safety and performance.

Primary Endpoint:

- Radiographic & clinical fracture healing at 3 months post-surgery.

Secondary Endpoints:

- Complications
- Radiologic & clinical fracture healing at 6 weeks, 3, 6, and 12 months post-surgery.
- Callus size & distribution at 6 weeks, 3, 6, and 12 months post-surgery.

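### An undefined non-compliance ground lets sites end observation of subjects who could still be examined, before healing or later complications are seen

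*Combined protocol and SAP*

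**What the plan says.** Section VI, Patient Withdrawal, opens its list with "The occurrence of any of the following situations gives reason to withdraw a patient from the study". One of the four items is "Patient is non-compliant". The protocol does not say what counts as non-compliance (visit attendance, weight bearing, other instructions), how much of it is needed, or when the ground may be used.

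What must be recorded is the Study Completion form: "In particular the reason for withdrawal must be documented". No final healing or complication assessment is required, and nothing says that outcomes are collected after withdrawal.

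The primary endpoint in Section III is "Radiographic & clinical fracture healing at 3 months post-surgery". The visit schedule in Section VI reads "Follow-up evaluations will be performed at 6 weeks (± 14 days), 3 months (± 14 days), 6 months (± 30 days) and 12 months (± 30 days) post-surgery", so a withdrawal decision can come before the primary visit.

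Under Minimization of Subjects Lost to Follow-Up, the same section states "The expectation is to maintain the highest rate of follow-up compliance possible throughout this study".

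Section VII plans frequencies and percentages for categorical data. It names no analysis set, no denominator, and no rule for missing or withdrawn subjects.

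**The concern.** In a drug trial, withdrawal may at least stop a treatment. Here there is no study treatment to stop: Section VIII says that participation is not expected to affect medical care, and the plate and screws remain in the leg. Withdrawing a subject for non-compliance therefore only removes information. Refusal by the patient, loss to follow-up and complete device removal each have their own provision, so what this ground mainly adds is the closing of subjects who can be reached and have not withdrawn consent.

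The investigator also reads the radiographs, the surgeon scores the FIX-IT, and no one else is assigned the non-compliance decision. That decision can therefore be taken with the 6-week result in hand. There is no control group in which the same selection would occur.

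At stake are the primary healing rate and the complication rate, the two results on which a statement about safety and performance would rest. An outcome that was never collected cannot be recovered at analysis.

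**Working it through.** **The plan's own figure.** Section VII expects 5 patients per site per year at 8 sites: 5 × 8 = 40, which reproduces. This is a feasibility count. Section V sets a floor of 30. No dropout rate, withdrawal rate or expected healing rate for this fracture is given, so every rate below is an assumption.

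**Set side by side.** For a removed device, Section VI (Recommended Revision Procedure) requires the radiographic findings and an Adverse Event CRF before the subject is terminated. For non-compliance it requires only a form and a reason. For a subject who cannot be reached, Section VI sets out phone calls, a letter, a certified letter and additional contacts before closure. These steps do not apply to a reachable subject judged non-compliant.

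**Healing.** Let N be the number enrolled, w the number withdrawn before 3 months, p_r the healing rate in those retained, and p_w the rate in those withdrawn. The reported rate is p_r. The rate over all enrolled is

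p_all = [(N − w)·p_r + w·p_w] / N.

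With N = 40, w = 4, p_r = 80% and p_w = 50%: (0.80 × 36 + 0.50 × 4)/40 = 30.8/40 = 77.0%. The report is 3 points too high.

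Range with p_r = 80% (rate over all enrolled, with the overstatement in points):

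| N, w | p_w = 80% | p_w = 60% | p_w = 40% | p_w = 20% |
|---|---|---|---|---|
| 40, 2 | 80% (0) | 79% (1) | 78% (2) | 77% (3) |
| 40, 4 | 80% (0) | 78% (2) | 76% (4) | 74% (6) |
| 40, 8 | 80% (0) | 76% (4) | 72% (8) | 68% (12) |
| 30, 4 | 80% (0) | 77.3% (2.7) | 74.7% (5.3) | 72.0% (8.0) |

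If withdrawn subjects healed better, say 90% with N = 40 and w = 4, then (28.8 + 3.6)/40 = 81.0% and the report would be 1 point too low.

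**Bounds that need no assumption about the withdrawn.** With x healed among those retained, the rate over all enrolled lies between x/N and (x + w)/N. For N = 40:
- w = 4: 29/36 = 80.6% reported; bounds 29/40 = 72.5% to 33/40 = 82.5%.
- w = 8: 26/32 = 81.3% reported; bounds 26/40 = 65.0% to 34/40 = 85.0%.

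**Complications.** Assume 10% in those retained and 50% in those withdrawn. With w = 4, (0.10 × 36 + 0.50 × 4)/40 = 5.6/40 = 14.0%, against 3.6/36 = 10% among those retained. With w = 2 the figure is (3.8 + 1.0)/40 = 12.0%, and with w = 6 it is (3.4 + 3.0)/40 = 16.0%. This treats every complication in the withdrawn as unseen. Section IX requires complications to be documented while the subject is in the study. If one of the two expected events came before withdrawal and was counted over all 40, the report would be (3.6 + 1)/40 = 11.5%.

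**Chance of seeing no fixation failure.** Assume risks of 3% (retained) and 20% (withdrawn), w = 4, and all failures in the withdrawn occurring after they leave. Over all 40 the chance is 0.97^36 × 0.80^4 = 13.7%. Among the 36 it is 0.97^36 = 33.4%. Expected failures are 0.03 × 36 + 0.20 × 4 = 1.88, of which 1.08 would be seen.

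**The case against.** The other side has several fair points.

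- **The wording is permissive.** A reader might infer that a non-compliant subject must be withdrawn. The list says only that these situations give reason to, and the reason is documented, so such withdrawals can be counted. This stands. It limits how often the ground will be used but does not bring back the outcomes.
- **Higher risk is not documented.** A reader might infer that non-compliant subjects are known to be more likely to suffer fixation failure. No section says so. Section II ties fracture-site motion to load bearing, and Section IV says that parallel motion is thought to favour symmetric callus, so the documents do not settle the direction. The follow-up text uses compliance for visit attendance, and patients who skip visits may be those who feel well. This stands: the bias is conditional.
- **Events before withdrawal are reported.** This stands, and it makes 10% against 14% the largest gap under those assumed rates, with the retained subjects as denominator.
- **The shift is small beside sampling error.** At 80% with 36 subjects the standard error is √(0.8 × 0.2/36) = 6.7 points, so 3 points is under half of it. This stands for that case. With 8 withdrawn and 40% healing in them, the shift is 8 points.
- **Loss to follow-up is not a one-visit rule.** The text reads "Patients will be considered lost to follow-up after they have missed a visit and a reasonable number of attempts to locate and evaluate them have" been unsuccessful, and the contact steps must be worked through first. The protocol is silent on a subject who later reappears; it does not forbid a return.

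Two further readings are unsupported. Non-replacement is stated for subjects lost to follow-up, not for withdrawn subjects. The separate ground "Development of a concurrent condition which would interfere with the patient's continued participation" has not been shown to be faulty and needs no change on this account.

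**Conclusion.** The point holds in a limited form. The protocol permits sites to end observation of reachable, consenting subjects on an undefined ground, at any time, with no last assessment and no later data collection. That works against the protocol's own follow-up aim, and Section VII contains nothing to offset it.

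The effect on the results is conditional. If non-compliance goes with poorer healing or more failures, healing is overstated and complications understated. With 4 to 8 of 40 withdrawn and healing 20 to 60 points lower in them, the overstatement is 2 to 12 points. If outcomes are the same, the bias is zero and only precision is lost. The number withdrawn and all rates are assumed, so these figures show scale and do not predict this study's error. The documents do not support saying that withdrawal is obligatory or that the bias is certain. The change is still worth making because it is cheap and the lost outcomes cannot be recovered.

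**What to change.** 1. Delete "Patient is non-compliant" from the withdrawal list in Section VI. Record non-compliance on the existing Protocol Deviation CRF. The Protocol Deviations text in Section IX speaks of departures by the investigator, so add a sentence that the form also covers subject non-compliance, and define the term.
2. State that healing and complication data continue to be collected through 12 months for every subject whose consent remains, whatever deviations are recorded. The rule on complete device removal is outside this point.
3. For loss to follow-up, keep the contact steps. Amend the Lost to Follow-up paragraph and the contact-attempts table together, so that a subject who reappears before the 12-month window closes can resume visits. Changing one alone would create a contradiction about when the Study Completion form is final.
4. In Section VII, report withdrawals by reason. Give healing over all enrolled and treated subjects, with best-case and worst-case rates counting subjects without a 3-month outcome as healed and as not healed.

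The cost is protocol wording and a short addition to the analysis. Sites will keep contacting a few difficult subjects until month 12, and some visits will be late or partial. Deleting the ground does not ensure that a retained subject attends at 3 months, which is why item 4 is needed as well.
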